6.2.1. Average Low Back Pain Intensity (LBPI) Score

Change from Baseline to Weeks 1, 2, 4, 8, 12, 16, 24, 32, 40, 48, 56 and 64 in average LBPI score.

For each treatment and each timepoint assessed, the endpoint will be summarized along with 95% CIs. Handling of missing data is described in [Section 5.3](#).

The ANCOVA model for change from baseline of aLBPI up to week 56 described in [section 5.2.2](#) will also be conducted. The plot of LS mean (+/- SE) for change from baseline up to week 56 will also be prepared.

LBPI data obtained after the early termination visit and considered as off-treatment will be shown in the listing and not be included in any summaries and analyses.

Cumulative distribution of percent change from Baseline in average LBPI score to Weeks 16, 24 and 56.

The cumulative aLBPI response at Weeks 16, 24 and 56 using response definitions from a reduction of >0% to =100% (in steps of 10%) will be summarized, using observed data, mixed BOCF/LOCF, and also LOCF and BOCF imputation for aLBPI (see [Section 5.3](#)).

Imputation with BOCF for subjects with missing data at that timepoint will lead to the subjects being assessed as non-responders for the response endpoint.

Plots of cumulative distribution of percent change from Baseline in average LBPI score to Week 16 and Week 56 (mixed BOCF/LOCF) will be created.

Response as defined by a $\geq 30\%$, $\geq 50\%$, $\geq 70\%$ and a $\geq 90\%$ reduction from Baseline in weekly average LBPI score derived from the subject diary at Weeks 16, 24, 40 and 56.

For each treatment and each timepoint assessed, the number and percentage of subjects in each response category endpoint will be summarized along with 95% CIs. Treatment differences of proportion of responder between each tanezumab treatment group versus celecoxib group will be estimated with 95% CI of Agresti-Caffo method. These analyses use observed data, mixed BOCF/LOCF, and BOCF and LOCF for missing data. The use of BOCF for missing data implies subjects with missing data are included in the analysis as non-responders. Similarly the use of LOCF in the case where subjects have no post-Baseline data (and Baseline would be carried forward) again implies those subjects are included in the analysis as non-responders.

6.2.2. Roland-Morris Disability Questionnaire (RMDQ) total score

Change from Baseline to Weeks 2, 4, 8, 16, 24, 32, 40, 48, 56 and 64 in the RMDQ total score.

For each treatment and each timepoint assessed, the endpoint will be summarized along with 95% CIs. Handling of missing data is described in [Section 5.3](#).

The ANCOVA model for change from baseline of RMDQ up to week 56 described in [section 5.2.2](#) will also be conducted. The plot of LS mean (+/- SE) for change from baseline up to week 56 will also be prepared.

Response as defined by a $\geq 30\%$, $\geq 50\%$, $\geq 70\%$ and a $\geq 90\%$ reduction from Baseline in the RMDQ score at Weeks 16, 24, 40 and 56.

For each treatment and each timepoint assessed, the endpoint will be summarized along with 95% CIs. These analyses use observed data, mixed BOCF/LOCF, and BOCF and LOCF for missing data. The use of BOCF for missing data implies subjects with missing data are included in the analysis as non-responders. Similarly the use of LOCF in the case where subjects have no post-Baseline data (and Baseline would be carried forward) again implies those subjects are included in the analysis as non-responders.

Cumulative distribution of percent change from Baseline in RMDQ score to Weeks 16 and 56.

The cumulative RMDQ response at Weeks 16 and 56 using response definitions from a reduction of $>0\%$ to $=100\%$ (in steps of 10%) will be summarized using mixed BOCF/LOCF imputation for RMDQ. Plots of cumulative distribution of percent change from Baseline in RMDQ score to Week 16 and Week 56 (mixed BOCF/LOCF) will also be created.

6.2.3. Patient's Global Assessment of Low Back Pain (PGA-LBP)

Change from Baseline to Weeks 2, 4, 8, 16, 24, 32, 40, 48, 56 and 64 in Patient's Global Assessment of Low Back Pain.

For each treatment and each timepoint assessed, the endpoint will be summarized along with 95% CIs. Handling of missing data is described in [Section 5.3](#).

Treatment Response: Improvement of ≥ 2 points in Patient's Global Assessment of Low Back Pain at Weeks 16, 24, 40 and 56.

For each treatment and each timepoint assessed, the endpoint will be summarized along with 95% CIs. Handling of missing data is same with [Section 5.3](#).

Treatment Response: Any improvement (change <0), no change (change $=0$), any worsening (change >0) at Weeks 16, 24, 40 and 56.

For each treatment and each timepoint assessed, the number and percentage of subjects in each category will be shown. Handling of missing data is same with [Section 5.3](#).

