The imputation of baseline-like data for subjects with missing data due to discontinuation due to Death, AE or LoE is intended to impute conservative efficacy values for those subjects who discontinue because of a reason that is considered to be a poor outcome for the subject, and so a poor outcome is imputed. For those subjects with missing data that is likely to not be related to treatment group, the intention is that missing data should be imputed based on a ‘missing at random’ assumption taking into account the subject’s previous available data.

One hundred imputed samples will be used in this analysis. In order to pre-define the analysis (and not to allow the results to change if run again), the following seeds will be used in the creation of the multiple imputed data: aLBPI: 1001-1100; RMDQ: 2001-2100; PGA-LBP: 3001-3100; BPI-sf scores for Worst Pain, Average Pain, Pain Interference Index (composite function score), Pain Interference with General Activity, Pain Interference with Walking Ability, Pain Interference with Sleep, and Pain Interference with Normal Work: 4001-4100. Imputed Week 16 and 56 data for the PGA-LBP will be rounded to integer scores in the range 1 to 5. Imputed Week 16 and 56 data for the aLBPI that are <0 and >10 will be truncated to 0 and 10, respectively.

Two additional methods will explore the sensitivity of the effect of missing data. The first method of Baseline Observation Carried Forward (BOCF) for missing data at Week 16 and 56 will impute the subject’s Baseline value for the Week 16 and 56 time point, respectively, and therefore a zero change from baseline. If a subject’s baseline data is also missing then that subject’s data remain missing for the post-baseline time point. The second method of Last Observation Carried Forward (LOCF) for missing data at Week 16 and 56 will impute the subject’s last observed data value for the efficacy endpoint. With LOCF, if a subject is missing all post-baseline efficacy data for a given efficacy endpoint, then baseline will be carried forward (if baseline is missing then the subject would have no contributing data to be included in the analysis).

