As for LBPI and RMDQ, ANCOVA with covariates described in [Section 5.2.2](#) will be conducted for all time points up to week 56. Study site will be fitted as a random effect in the ANCOVA model. This analysis will use multiple imputation for missing data as described above. While the table describes the multiple imputation strategy specific for the Week 16 time point, it also applies to all other analysis time points, eg, ‘Week 2’ would be substituted for ‘Week 16’ in the above table, to describe the Week 2 multiple imputation strategy.

The responder endpoints will be summarized, using both BOCF and LOCF for missing data of the response endpoint at a particular time point. Imputation using BOCF will lead to the subject being assessed as a non-responder. In addition, a mixed BOCF/LOCF imputation for response endpoints will be used. In this analysis BOCF imputation (ie, a subject would be a non-responder) would be used for missing data due to discontinuation for reasons of lack of efficacy, patient's not meeting protocol-specified pain criteria, adverse event or death up to the time point of interest, and LOCF imputation would be used for missing data for any other reason.

Note, if Baseline is missing then the subject data for the change from Baseline will be set to missing for all efficacy analyses for that parameter. A subject who has a missing Baseline score will be missing for the response criteria for endpoints where the response is based on one parameter.

The CLBP-RI (Chronic Low Back Pain Responder Index) is based on 3 parameters (aLBPI, RMDQ and PGA-LBP). It is set to missing if any one out of these three parameters are missing at baseline or for the relevant post-Baseline timepoint (per its definition, a response can still be achieved if all three component parameters meet certain criteria).

For the RMDQ, any missing items are treated as the patient not having that symptom, and so not included in the RMDQ total score.

The BPI-sf Pain interference index score is calculated from the seven BPI-sf pain interference items. The composite index score is calculated as the mean of the non-missing items as long as ≥ 4 of the 7 items are non-missing, otherwise (≤ 3 items non-missing) the index score is missing.

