| Change from Baseline to Weeks 16 and 56 in the BPI-sf Pain Interference with Normal Work | ITT | None (summary) | NA | LOCF | Secondary Endpoint Analysis |
| The CLBP-RI response at Weeks 16, 24, 40 and 56 | ITT | None (summary) | NA | Observed | Secondary Endpoint Analysis |
| The CLBP-RI response at Weeks 16, 24, 40 and 56 | ITT | None (summary) | NA | Mixed BOCF/LOCF | Secondary Endpoint Analysis |
| The CLBP-RI response at Weeks 16, 24, 40 and 56 | ITT | None (summary) | NA | BOCF | Secondary Endpoint Analysis |
| The CLBP-RI response at Weeks 16, 24, 40 and 56 | ITT | None (summary) | NA | LOCF | Secondary Endpoint Analysis |
| Percentage of subjects with an improvement of ≥ 2 points from Baseline to Weeks 16, 24, 40 56 in the PGA-LBP | ITT | None (summary) | NA | Observed | Secondary Endpoint Analysis |
| Percentage of subjects with an improvement of ≥ 2 points from Baseline to Weeks 16, 24, 40 56 in the PGA-LBP | ITT | None (summary) | NA | Mixed BOCF/LOCF | Secondary Endpoint Analysis |
| Percentage of subjects with an improvement of ≥ 2 points from Baseline to Weeks 16, 24, 40 56 in the PGA-LBP | ITT | None (summary) | NA | BOCF | Secondary Endpoint Analysis |
| Percentage of subjects with an improvement of ≥ 2 points from Baseline to Weeks 16, 24, 40 56 in the PGA-LBP | ITT | None (summary) | NA | LOCF | Secondary Endpoint Analysis |
| Percentage of subjects with any improvement (change <0), no change (change=0), any worsening (change >0) in the PGA-LBP at Weeks 16, 24, 40 and 56 | ITT | None (summary) | NA | Observed | Secondary Endpoint Analysis |

| | | | | | |
|--|-----|----------------|----|-----------------|-----------------------------|
| Percentage of subjects with any improvement (change<0), no change (change=0), any worsening (change>0) in the PGA-LBP at Weeks 16, 24, 40 and 56 | ITT | None (summary) | NA | Mixed BOCF/LOCF | Secondary Endpoint Analysis |
| Percentage of subjects with any improvement (change<0), no change (change=0), any worsening (change>0) in the PGA-LBP at Weeks 16, 24, 40 and 56 | ITT | None (summary) | NA | BOCF | Secondary Endpoint Analysis |
| Percentage of subjects with any improvement (change<0), no change (change=0), any worsening (change>0) in the PGA-LBP at Weeks 16, 24, 40 and 56 | ITT | None (summary) | NA | LOCF | Secondary Endpoint Analysis |
| Time to discontinuation due to lack of efficacy (up to Week 56/End of Treatment) | ITT | KM estimates | NA | Observed Data | Secondary Endpoint Analysis |

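### In the three-category PGA-LBP table, BOCF and mixed BOCF/LOCF show imputed subjects as 'no change', which biases the 'any worsening' row downward

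*SAP*

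**What the plan says.** SAP 6.2.3 defines three categories of change in PGA-LBP: below zero is improvement, zero is no change, above zero is worsening. For each arm and each of Weeks 16, 24, 40 and 56, "the number and percentage of subjects in each category will be shown. Handling of missing data is same with" Section 5.3.

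Appendix 1 lists four versions of this table: observed, mixed BOCF/LOCF, BOCF and LOCF. The mixed row, for example, reads "in the PGA-LBP at Weeks 16, 24, 40 and 56 | ITT | None (summary) | NA | Mixed BOCF/LOCF".

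SAP 5.3 supplies the rules:

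- BOCF imputes the Baseline value, "and therefore a zero change from baseline". This is written for Weeks 16 and 56, but carrying Baseline forward has the same arithmetic at Weeks 24 and 40.
- For responder endpoints, "Imputation using BOCF will lead to the subject being assessed as a non-responder".
- Under the mixed rule, "BOCF imputation (ie, a subject would be a non-responder) would be used for missing data due to discontinuation for reasons of lack of efficacy". The same applies to pain-criterion failure, adverse event and death. LOCF is used for any other reason.

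Section 5.3 has no separate rule for an outcome with three categories. SAP 6.2 excludes off-treatment windows (more than 8 weeks after the window of the last SC dose) from treatment-period summaries, so later visits of subjects who stop become missing and are imputed.

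**The concern.** Non-responder is a yes/no idea. It fits the improvement row, where a subject with zero change counts as not improved. It does not carry over to a table that also reports deterioration, because zero change is a category of its own there and reads as stable.

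Under full BOCF this happens to every subject with a missing value, whatever the reason. Under the mixed rule it happens to those who stopped for lack of efficacy, pain criteria, an adverse event or death. At the imputed visits, mainly Weeks 24, 40 and 56, none of them can appear as worsened. The more subjects an arm loses this way, the fewer remain who could be counted as worse. Someone comparing the worsening row across arms could be misled, and deaths would be displayed as stable pain status.

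**Working it through.** **Share imputed.** Protocol 9.1 multiplies the Week 16 responder rate by retention afterwards:

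- OA studies: 0.60 × 0.90 = 54%.
- CLBP study: 0.42 × 0.80 = 33.6%, stated as about 34%.

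Table 6 follows by rounding down. For this study alone, 113 × 0.34 = 38.4 and 146 × 0.34 = 49.6 give 38-49; 113 × 0.54 = 61.0 and 146 × 0.54 = 78.8 give 61-78. The plan's figures are reproduced.

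Non-completers are therefore 46% to 66%, or about 30 to 44 of 66 per arm. This is an upper limit on what is imputed at Week 56. A subject who stops after the Week 48 dose has Early Termination Visit 1 eight weeks later, with PGA collected (Protocol Table 2), inside the on-treatment window. By the same figures, 40% to 58% would miss the 30% response level at Week 16 (about 26 to 38 of 66).

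**Algebra.** Let f be the share imputed by BOCF, wc the worsening rate among subjects still observed, and wf the rate among those imputed.

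- Actual worsening = (1 − f)·wc + f·wf
- Shown under BOCF = (1 − f)·wc
- Understatement = f·wf

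The understatement grows with f, and the displayed row falls as f rises. If wc and wf are the same in two arms and wf exceeds wc, the arm with more failures has more actual worsening but shows less.

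**Illustration for full BOCF at Week 56.** The documents give no PGA worsening rates. Assume wc = 5%, and let wf be the share of stopped subjects who were worse than Baseline at their last on-treatment visit. With completer share c:

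- LOCF = c × 5% + (1 − c) × wf
- BOCF = c × 5%

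| wf (assumed) | LOCF, c = 34% | LOCF, c = 54% | BOCF, c = 34% | BOCF, c = 54% |
|---|---|---|---|---|
| 0% | 1.7% | 2.7% | 1.7% | 2.7% |
| 10% | 8.3% | 7.3% | 1.7% | 2.7% |
| 20% | 14.9% | 11.9% | 1.7% | 2.7% |
| 30% | 21.5% | 16.5% | 1.7% | 2.7% |

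**Mixed rule.** Protocol 9.1 puts losses after Week 16 at 0.42 × 0.20 = 8.4% (CLBP) and 0.60 × 0.10 = 6% (OA) of subjects. Suppose all of these are imputed by LOCF and all Week 16 failures by BOCF. At wf = 20% the worsening row is:

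- CLBP: 0.336 × 5% + 0.084 × 20% = 3.4%
- OA: 0.54 × 5% + 0.06 × 20% = 3.9%

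Full LOCF gives about 15% and 12%. Any later loss due to an adverse event or death would move to BOCF and lower the mixed figures. The distortion is smaller than under full BOCF but remains.

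**The case against.** The mechanism is hard to dispute. The case on the other side concerns its weight, and much of it stands.

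- **The table carries little.** SAP 5.1 says that no hypotheses are tested, and this table has counts and percentages only, with no treatment difference. The three-way split is not among the protocol's secondary endpoints. Observed and LOCF versions are produced alongside. Discontinuation for lack of efficacy is reported directly in SAP 6.2.8, with differences, intervals and Kaplan-Meier estimates, and disposition by reason is in 6.5.2.
- **Failing the Week 16 criterion is not worsening.** A subject whose pain fell by 10-29% fails it. For anyone not worse than Baseline, the no-change label does not understate worsening. Subjects entering at PGA grade 5 cannot worsen at all. A low wf is therefore possible, and at wf = 0 there is no understatement.
- **Week 16 is largely spared.** A subject last dosed at Week 8 normally still has an on-treatment Week 16 PGA.

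A reader might also infer that the rule contradicts the SAP's own stated purpose, since Section 5.3 speaks of "a reason that is considered to be a poor outcome for the subject, and so a poor outcome is imputed". The documents do not support that. The sentence explains the baseline-like multiple imputation; BOCF is introduced separately as a sensitivity method.

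A footnote could prevent misreading, but it would leave the percentages in the worsening row as they are.

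**Conclusion.** The point holds as a flaw in two of the four planned versions of one descriptive table. Followed as written, the BOCF and mixed versions show imputed subjects, including deaths, as unchanged, and bias the worsening row downward by f·wf. This follows from the SAP text and needs no assumption beyond some of the imputed subjects having truly worsened. The improvement row is conservative, as one would want.

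The size is illustrative. With 5% worsening assumed in completers and 10-30% in those who stopped, full BOCF shows about 2-3% against about 7-22% under LOCF. LOCF is a comparator here and not the truth.

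A reader might infer from the table above that the arms will be shown in the wrong order. The documents do not establish this. The 34% and 54% are estimates from different earlier studies and not a forecast contrast between arms, and reversal also needs more worsening among those who stopped than among those who stayed. The BOCF figures of 1.7% and 2.7% are about 1.1 and 1.8 subjects of 66. Reversal is possible; the plan does not show that it is likely.

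**What to change.** In the BOCF and mixed BOCF/LOCF versions of this table, replace the imputed no-change entries with a fourth row:

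- **Mixed BOCF/LOCF:** discontinued for lack of efficacy, pain criteria, adverse event or death. Subjects imputed by LOCF stay in the category that their last value gives.
- **Full BOCF:** missing/discontinued, for any reason.

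Keep these subjects in the denominator and count them as not improved, so that the improvement row does not change. Amend SAP 6.2.3 and the two matching Appendix 1 rows. Leave the observed and LOCF versions alone.

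The cost is a few lines of SAP text and one extra row per table. The no-change percentages become smaller. No new data or model is needed.

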6.2.4. Brief Pain Inventory-short form (BPI-sf) scores

Change from Baseline to Weeks 2, 4, 8, 16, 24, 40, 56 and 64 in the BPI-sf scores for Worst Pain, Average Pain, Pain Interference Index (composite function score), Pain Interference with General Activity, Pain Interference with Walking Ability, Pain Interference with Sleep, and Pain Interference with Normal Work.

For each treatment and each timepoint assessed, the endpoint will be summarized along with 95% CIs. Handling of missing data is described in [Section 5.3](#).

6.2.5. Chronic Low Back Pain Responder Index (CLBP-RI) Analysis

CLBP-RI analysis [composite endpoint of average LBPI score, Patient's Global Assessment of Low Back Pain, and RMDQ total score] at Weeks 16, 24, 40 and 56.

For each treatment and each timepoint assessed, the endpoint will be summarized along with 95% CIs. Handling of missing data is same with [Section 5.3](#).

Plot of CLBP-RI analysis at week 16, 24, 40 and 56 (mixed BOCF/LOCF) will be created.

6.2.6. Euro Quality of Life Health State Profile (EQ-5D-5L™)

EQ-5D-5L™ dimensions and overall health utility score at Baseline, Weeks 16 and 56

The Baseline and Weeks 16 and 56 responses in the five dimensions (mobility; self-care; usual activity; pain/discomfort; anxiety/depression) and overall health utility score from the EuroQol 5 Dimensions (EQ-5D-5L) will be summarized by treatment group. This summary will use observed data only (no imputation for missing data). The calculation of the overall health utility score is described in [Appendix 2.3](#).

An additional question, called the EQ-VAS asks the patient to rate their health today using a VAS scale from 0 (the worst health you can imagine) to 100 (the best health you can imagine). This will be summarized along with the health utility score.

A table showing number and percentage of subjects will summarize the response for each dimension (item) of the EQ-5D-5L at each timepoint. These summary tables will be shown by treatment group. In addition, for each treatment and each time point assessed, descriptive statistics (mean, standard deviation, median, minimum, maximum, number of subjects) will be shown for the health utility score, and the EQ-VAS measure of health today.

